6.11.3 Data Monitoring for Harm

6.11.3.1 Safety reporting

Definitions of harm of the EU Directive 2001/20/EC Article 2 based on the principles of ICH GCP apply to this trial.

This is a low-risk intervention. No specific risks, or adverse events were reported during feasibility testing of the intervention[22]. Any non-serious untoward incidents occurring during this trial (e.g. clear evidence of high levels of distress making participants difficult to continue with the study) will be recorded in an incident report form which will be monitored for frequency and severity. The participant's GP will also be informed to contact NCTU if they become aware of any adverse event during the study such as significant deterioration in mental health and they feel that the participant should no longer be taking part in the study. Serious adverse events (SAE) will be collected using an SAE form.

Table 3: Serious Adverse Event Definitions

Serious Adverse Event (SAE)	Any adverse event that:
	 results in death; is life threatening*; requires hospitalisation or prolongs existing hospitalisation**; results in persistent or significant disability or incapacity.
	The most likely SAE to occur in this study is new reports of active suicidal ideation with active suicidal behaviours/plans and imminent intent.

* The term life threatening here refers to an event in which the patient is at risk of death at the time of the event; it does not refer to an event that might hypothetically cause death if it was more severe (e.g. a silent myocardial infarction).

** Hospitalisation is defined as an in-patient admission, regardless of length of stay, even if the hospitalisation is a precautionary measure for continued observation. Hospitalisation for preexisting conditions (including elective procedures that have not worsened) do not constitute an SAE.

Serious adverse events do NOT include:

- Pre-existing disease or a physical health condition present before trial treatment;
- An exacerbation of such pre-existing physical illness (e.g. cancer) during the trial;
- A physical health condition that is detected after trial treatment.

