4.3 Sample size

Participants in our feasibility study had an average reduction of 26% on GAD-7. A reduction of 20% on GAD-7 is considered to be a Minimum Clinically Important Difference [13]. Using a conservative reduction of 20% from the mean baseline GAD-7 score, and using the variability estimated from our feasibility study, a clinically-meaningful effect size is estimated to be d = 0.55 for our sample. Recent systematic reviews of RCTs of self-help ACT and mindfulness-based interventions (mainly for individuals with a mental or physical health condition) demonstrated a pooled effect size of d = 0.35 for anxiety [14, 15]. One of these reviews, which solely focused on RCTs of self-help ACT [14] demonstrated that when analysis was limited to studies that utilised guided self-help ACT, the pooled effect size increased to d = 0.61, while limiting analysis to studies that used an unguided approach decreased the pooled effect size to d = 0.16. The effect size calculated from our feasibility study of iACT4CARERS, which utilised a guided approach, is in line with the effect size reported in previous reviews.

To ensure adequate statistical power, we have decided to take the most conservative approach possible and have used an effect size of d = 0.35 in our sample size calculation. To detect the effect size of d = 0.35between the two trial arms at a two-tailed significant level of 5% with 90% statistical power, each arm requires 173 participants (i.e. 346 in total). Twenty seven percent of carers were lost to follow-up in our feasibility study. Assuming a dropout rate of 30%, a total of 496 carers will be recruited over 20 months (i.e. 24.8 participants per month).

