4.6 Timing of outcome assessments

The primary outcome is anxiety symptoms as assessed by the Generalized Anxiety Disorder-7 (GAD-7) at 12 weeks. The GAD-7, a validated self-report questionnaire [16], is the routine outcome monitoring tool for measuring anxiety symptoms used in the NHS. The GAD-7 will be completed at baseline, at 12 weeks post-randomisation and at 24 weeks post-randomisation.

5. Statistical Principles

All hypothesis testing will be at the two-sided 5% statistical significance level. Confidence intervals for parameter estimates will be at the corresponding 95% level. Analyses will be carried out by the trial statistician or delegated to an appropriately skilled statistician. Analysis will be blinded to group identity, (i.e. 'subgroup' blind). The Statistical Analysis Plan (this document) will be approved by the trial Data

Monitoring and Ethics Committee (DMEC) and the Trial Steering Committee (TSC) prior to any data analyses by the trial statistician. The lead health economist will develop a Health Economics Analysis Plan (HEAP) separately, which will also be reviewed by the DMEC and the TSC. Thus, the process for an economic evaluation is not described in this document. The process evaluation, including qualitative data analyses of interview transcripts, will be undertaken independently from the primary data analysis outlined in the SAP. Therefore, these procedures have not been described in this document.

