7.6 Safety data

Safety data (adverse events reported from time of first exposure to treatment to end of treatment) will be summarised by group. Any serious adverse events will be described in full including possible relationship to the treatment.

Serious adverse events related or unrelated to the intervention, will be analysed using a logistic regression model with the random effects, pre-specified prognostic variables and treatment group as explanatory variables.

8. Description of Tables and Figures

All data up to the time of study completion/withdrawal from the study will be included in the analysis, regardless of duration of treatment.

All raw data will be presented to the original number of decimal places. The mean and standard deviation will be presented with to 2 decimal places or 3 significant figures depending upon the nature of the data. Percentages will be presented in to 1 decimal place. All categories of variables will be presented even if there is no data. Blank cells, were data are not expected, will be filled by "-" in reporting of results.

Precision of p-values will be 3 decimal places, i.e. p-values less than 0.001 will be presented as <0.001 and if equal to 1 then \ge 0.999.

9. Software

All analysis will be performed using SAS[®] Software version 9.4 and Stata version 17.

10. References

- 1. Collins, R. and N. Kishita, *Prevalence of depression and burden among informal caregivers of people with dementia: A meta-analysis.* Ageing and Society, 2020. **40**(11): p. 2355-2392.
- 2. Kaddour, L. and N. Kishita, *Anxiety in informal dementia caregivers: a meta-analysis of prevalence.* Journal of Geriatric Psychiatry and Neurology, 2020. **33**(3): p. 161-172.
- 3. McManus, S., et al., eds. *Mental health and wellbeing in England: Adult psychiatric morbidity survey 2014*. 2016, NHS Digital: Leeds, UK.
- 4. National Institute for Health and Care Excellence, *NICE guideline [NG97] Dementia: assessment, management and support for people living with dementia and their carers*. 2018, NICE: London, UK.
- 5. Alzheimer's Society, *Dementia 2014: Opportunity for change*. 2014, Alzheimer's Society: London, UK.
- 6. A-Tjak, J.G.L., et al., A meta-analysis of the efficacy of acceptance and commitment therapy for clinically relevant mental and physical health problems. Psychotherapy and Psychosomatics, 2015. **84**(1): p. 30-36.

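### SAP 7.6 names no test and no sparse-count method for its only inferential comparison of serious adverse events, so an arm with no events leaves no usable estimate or interval

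*SAP*

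**What the plan says.** Protocol 6.5.2 lists SAEs among the secondary outcomes. SAP 7.6 treats them in two layers.

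- **Descriptive.** Safety data "will be summarised by group. Any serious adverse events will be described in full including possible relationship to the treatment".
- **Inferential.** SAEs "will be analysed using a logistic regression model with the random effects, pre-specified prognostic variables and treatment group as explanatory variables".

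The random effects are presumably those of SAP 7.2: site, and therapist nested within site. SAP 7.6 does not list the prognostic variables. It does not say whether treatment is tested by Wald or likelihood ratio, sets no minimum event count, and gives no exact, penalised or unadjusted fallback and no absolute-risk measure. SAP section 5 adds the general rule: "All hypothesis testing will be at the two-sided 5% statistical significance level", with 95% intervals to match.

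On how many SAEs to expect, Protocol 6.11.3.1 calls the intervention low-risk and reports "No specific risks, or adverse events were reported during feasibility testing of the intervention". That feasibility study recruited 33 carers (Protocol 5.1). The list under Table 3 of events that are not SAEs covers pre-existing disease, exacerbation of pre-existing physical illness, and "A physical health condition that is detected after trial treatment". Table 3 names new active suicidal ideation with plans or behaviours and imminent intent as the likeliest SAE, while Protocol 6.3.1.3 excludes carers who express active suicidal intent at screening. No expected SAE rate appears in either document.

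**The concern.** A logistic model with covariates and two levels of clustering needs a reasonable number of events. The documents point to few. With very few events, one arm may have none, and then maximum likelihood has no finite estimate for the treatment effect. What gets reported depends on which test the analyst takes from the output, and the SAP does not say. The analysis is then least informative when the split between arms is most one-sided, and the report would carry no usable statement of how large an excess risk the trial can exclude.

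**Working it through.** **The plan's own figure.** The documents give no SAE rate, power or test, so the only figure to reproduce is the arm size. SAP 4.3 says the authors "have used an effect size of d = 0.35 in our sample size calculation", at a "two-tailed significant level of 5% with 90% statistical power, each arm requires 173 participants (i.e. 346 in total"). The normal formula 2(1.960 + 1.282)²/0.35² gives 171.5. The t-based version gives 172.5, hence 173 per arm. For dropout, 346/0.70 = 494.3, so 495, or 496 as two equal arms of 248. This agrees with the SAP: "Assuming a dropout rate of 30%, a total of 496 carers will be recruited over 20 months". Below, all 248 randomised carers per arm are counted.

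**Chance that an arm has no SAE.** For SAE risk p this is (1 − p)^248. The risks are assumptions: 0.25% gives 54%, 0.5% gives 29%, 1% gives 8% and 2% gives 0.7%.

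**What the model returns at 8 v 0.**

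- *Maximum likelihood and Wald.* The odds ratio is (8 × 248)/(0 × 240), which has no finite value. A fixed-effects fit with treatment only stops wherever the software stops:
  - 8 iterations: Wald p = 0.36.
  - 15 iterations: log odds ratio 12.8, SE 209.5, p = 0.951.
  - 25 iterations: log odds ratio 22.8, SE about 31,000, p = 0.999.
- *Fisher.* 2 × C(248,8)/C(496,8) = 0.0074.
- *Likelihood ratio.* The log-likelihood with separate risks is 8 ln(8/248) + 240 ln(240/248) = −35.34. With a common risk it is 8 ln(8/496) + 488 ln(488/496) = −40.95. Twice the difference is 11.22 on 1 df, p = 0.0008.

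**Other splits, 248 per arm** (treatment-only fits; Wald after 25 iterations):

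| SAEs | Wald p | Likelihood-ratio p | Fisher p | Firth p (log OR) |
|---|---|---|---|---|
| 3 v 0 | 0.999 | 0.041 | 0.25 | 0.11 (1.96) |
| 6 v 0 | 0.999 | 0.0038 | 0.030 | 0.013 (2.59) |
| 8 v 0 | 0.999 | 0.0008 | 0.0074 | 0.0031 (2.87) |
| 10 v 0 | 0.999 | 0.0002 | 0.0018 | 0.0007 (3.09) |
| 8 v 1 | 0.048 | 0.012 | 0.037 | 0.019 (1.76) |

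A single event in the second arm restores the Wald test. At 3 v 0 the likelihood-ratio test is significant while Fisher and Firth are not, so it is not a neutral default at very small counts either.

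**With clustering.** A fit with a site random intercept (20 equally likely sites) and one baseline covariate gave Wald p = 0.995, 0.997 and 0.997 at 6, 8 and 10 v 0. The likelihood-ratio p-values were 0.0037, 0.0009 and 0.0002. Therapist nesting and ethnicity terms were not fitted.

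**An interval that works.** The 95% score interval for the risk difference is 0.9% to 5.2% at 6 v 0 and 1.6% to 6.2% at 8 v 0.

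**How often it matters.** All pairs of binomial counts at 248 per arm were enumerated, with an empty arm counted as non-significant by Wald. The chance of at least one empty arm is 1 − [1 − (1 − p₁)^248][1 − (1 − p₂)^248].

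| Assumed risks | An arm empty | Wald p < 0.05 | Fisher p < 0.05 | Fisher significant, Wald not |
|---|---|---|---|---|
| 0.4% v 2% | 37% | 5.3% | 19.2% | 14% |
| 1% v 3% | 8% | 18.6% | 23.6% | 6% |
| 2% v 4% | 0.7% | 19.7% | 17.6% | 0.6% |

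Every outcome in the last column has an empty arm, so the loss is confined to that case.

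**The case against.** The strongest reply has five parts.

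1. **The arms are also compared descriptively.** A reader might infer that a clear harm signal could disappear behind a non-significant p-value. SAP 7.6 does not support that. An 8 v 0 split would be printed by group with every case described, and the SAP nowhere says it will conclude that the arms do not differ. The data monitoring committee also sees unblinded comparative data (Protocol 6.11.4.4.4). This stands. What is missing is a valid estimate and interval.
2. **The SAP does not specify a Wald test.** A likelihood-ratio test of the same model detects the imbalance. This stands too, so it cannot be said that the model necessarily fails. But SAP 7.2 names the likelihood-ratio test only for the random effects. Leaving the choice open between 0.0008 and 0.999 on the same data is the gap.
3. **Low power is not the model's fault.** Wald misses 81% of true excesses at 1% v 3% and 80% at 2% v 4%, and a reader might blame the method. Fisher misses 76% and 82%. Those figures come from rare events and sample size.
4. **Covariates and random effects.** A reader might infer that empty ethnicity levels break the arm comparison. An empty level affects that level's own coefficient, not the treatment coefficient, and the covariate list and ethnic mix are not given. SAP 7.2 also drops random effects that do not improve fit, if that rule carries over.
5. **SAP 7.5 permits other methods if documented.** That clause is generic and would be used after the data are seen. It does not pre-specify anything.

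**Conclusion.** The point holds as a gap in specification. SAP 7.6 makes an adjusted random-effects logistic model the sole inferential SAE comparison, names no treatment test, and has no method for sparse or zero counts that its own background makes foreseeable. When an arm is empty, the odds ratio and Wald interval are unbounded and the p-value turns on an unstated choice.

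The size depends on an SAE risk that the documents do not give. Measured by how often Fisher is significant and Wald is not, it runs from 14% of trials (0.4% v 2%) through 6% (1% v 3%) to 0.6% (2% v 4%). It matters mainly if SAE risk in the lower-risk arm is about 1% or less. These figures assume 248 counted per arm and independent carers. The documents do not support saying that harm would be concealed or that the planned model must give a p-value near 1. The change is still worth making, because it costs little and can only be pre-specified before analysis.

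**What to change.** In SAP 7.6, define the main SAE comparison as:

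- the number and percentage of randomised carers with at least one SAE, by arm;
- the risk difference with a 95% score or exact interval;
- an exact or Firth-penalised odds ratio with treatment as the only term.

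Keep the adjusted mixed logistic model as a supporting analysis, used only when event counts allow. State the count threshold, list the prognostic variables, and name the likelihood-ratio test for treatment.

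The cost is SAP wording; no data collection changes. The downside is that the main SAE comparison is unadjusted and ignores clustering by site and therapist, which a handful of events could not support in any case.
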